General overview: The proposed research will test in a nested case-control study associations of individual metabolites and broader metabolomics profiles as well as counter-regulatory hormones and biomarkers with stress-hyperglycemia (Aim 1). For this analysis patients will be stratified according to the outcome of stress-hyperglycemia (cases) and compared to controls (no hyperglycemia). For Aim 2 a randomized clinical trial will be conducted to examine the effects of exposure to dulaglutide on the prevention of stress-hyperglycemia and the metabolic inflammatory response in the perioperative period, (Fig. 6).

[figure not shown]

Figure 6. General overview. Aim 1 will be tested with a case-control study design. In Aim 2 we will conduct a clinical trial.

Specific Aims

D1. Case – control study

Aim 1. To examine baseline and postoperative metabolic profiles of non-diabetic CABG patients with stress hyperglycemia.

Rationale: the underlying mechanisms leading to stress-hyperglycemia and its association with poor outcomes in cardiac surgery patients are not well understood. We aim to study metabolic signatures associated with hyperglycemia and path-specific biomarkers. We will test the temporal relationships between candidate metabolites/pathways (Table 1) and specific biomarkers with stress-hyperglycemia.

Study design: In a nested case-control study (N=50) we will compare the characteristics of patients developing postoperative stress-hyperglycemia (cases) compared to patients that do not develop stress-hyperglycemia (age-matched controls). A proportion of patients will be derived from the placebo arm of the randomized trial. This design will allow efficient recruitment from our cohort of CABG patients to allow substantial savings in cost

and time. **Case definition:** stress-hyperglycemia is defined as a BG >140mg/dl on arrival to the ICU. Please see additional details in Human Subjects section.

Study Population: we will include patients with ages between 18-80 years without a history of diabetes [BG \leq 125 mg/dl and HbA1c <6.5%] undergoing CABG surgery. Patients will be recruited from three academic hospitals, including Emory University Hospital, Emory Hospital Midtown (EUHM), and Grady M Hospital in Atlanta, GA. [name] (Chief of Division and Director of the CTS Center for Clinical Research) is a key collaborator and will facilitate recruitment and perform CABG surgeries.

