With advanced data extraction provided by xMSanalyzer and apLCMS, I will be able to also measure a spectrum of high and low abundance metabolites. We will utilize a well-established computational metabolomics workflow with rigorous standard operating procedures outlined in Fig. 7.¹²⁴ Data Selection and Annotation (Biostatistics and Bioinformatics Tools): HRM data will be processed using apLCMS with xMSanalyzer^{125,126}. Feature annotation will be performed using xMSannotator.¹²⁷ xMSannotator provides confidence scores for more than 2,000 metabolites, with more than 300 metabolites having confirmed identities and including most major pathways. The quality of data will be judged based on established rigorous criteria (e.g. coefficient of variation within replicates and QC samples, the percentage of missing values, the percentage of data exceeding detection limits of the machinery, batch-effects, and the percentage of outliers, etc.). Principal Component Analysis (PCA) will be used for batch-effect evaluation and ComBat¹²² will be used for batch- effect correction if necessary. Identifying expressed metabolites across different time points: we will use univariate and multivariate statistical methods, such as linear mixed effects models with post-hoc Tukey tests, LIMMA, and multilevel sparse Partial Least Squares Discriminant Analysis (msPLSDA).^{128,129} Multiple hypotheses testing correction will be performed using the Benjamini-Hochberg method.¹³⁰ Identifying putative biomarkers: we will use a consensus feature selection approach such that metabolic signatures identified by both univariate and multivariate approaches will be used for downstream analyses. K-fold and leave-one-out cross-validation using Support Vector Machine (SVM) will be performed to evaluate predictive accuracy of putative biomarkers. Two-way hierarchical clustering analysis will be performed to identify clusters of correlated metabolic features and to evaluate the ability of the discriminatory features to separate samples based on stress-hyperglycemia. Pathway enrichment analysis: Pathway analysis will be performed with pathway enrichment software for untargeted metabolomics data (Mummichog and MetabNet)^{131,132}. Where appropriate, additional chemical verification will be performed for significant metabolites of interest according to retention time and characteristic ion dissociation (MS/MS) patterns relative to authentic standards. Metabolome-wide association study (MWAS) of specific metabolites will be conducted (MetabNet) to facilitate detection of their related metabolic pathways and network structures in association with glucose levels (continuous) and stress-hyperglycemia as a discrete dichotomous variable.

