
Expected outcomes of Aim 1: During our analysis of candidate metabolites and discovery phase in Aim 1 we expect to find an association between candidate metabolites (i.e. BCAA, ceramides, acylcarnitines) and pathways associated with stress-hyperglycemia. We also expect to find an association between pathway-

specific biomarkers and stress-hyperglycemia with a higher degree of association according to the number of biomarkers based on pre-specified cut points (biomarker risk score).⁶⁶ We expect to find multilevel associations between glucose, biomarkers and candidate metabolites. Serial measurements including measurements before the acute stress episode will facilitate causal interpretations.

Potential Pitfalls, and Alternative Considerations: It is possible that some comparisons do not yield false discovery rate (FDR)-significant metabolites. In this scenario, and to provide a balance between type I and type II statistical error, metabolites with raw $p < 0.05$ will be used for subsequent analyses, with statistical tests for pathway enrichment. Pathway enrichment analysis is less susceptible to type II error.¹³⁴ We hypothesize that stress-hyperglycemia leads to elevation of path-specific biomarkers, however it is possible that pre-surgical elevation of biomarkers predicts the development of stress-hyperglycemia. Elucidating this scenario is important as identifying susceptible subjects before surgery (baseline elevation of biomarkers) will facilitate the design of cohort studies as well as recruitment of at-risk patients in future trials.

D2. Randomized Clinical Trial

Aim 2. To obtain preliminary estimates of the effect of a long-acting GLP-1 RA on the prevention of stress-hyperglycemia and modulation of metabolic stress during cardiac surgery.

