- **Group Assignment / Case Definition:** Clinically stable adults scheduled to undergo coronary artery bypass graft surgery (CABG) will be studied. For logistic purposes recruitment will favor assignment to the clinical trial in the beginning of the award period (Aim 2, N=60). We expect a total of 30 subjects will be randomized to each group (dulaglutide or placebo). Thirty patients assigned to placebo in the clinical trial will contribute to the cohort of patients to be included in the nested case-control study. Cases and controls will be categorized prospectively on arrival to the surgical intensive care unit (SICU) (Cases are defined as BG >140mg/dL on ICU arrival). To further avoid selection bias, 25 age-matched controls will be selected for comparison. Once the number of cases is completed, additional potential controls will be selected (+/- 3 years) based on the characteristics of the population of cases. If additional patients develop stress hyperglycemia no further samples will be collected. This design will allow for efficient recruitment from our cohort of CABG patients to allow substantial savings in cost and time.
- **Research Sites:** All human subjects' research will be performed on the campus of Emory University, Atlanta, GA, and at Emory Affiliated Hospitals. Sites include Clinical Research Units (CTSA) where samples will be stored. Data collected are kept confidential and protected as per HIPAA regulations. Data collected at each facility will be shared only with the study team.

E.1.2. Study Endpoints and Sources of Materials:

- In the case control study (Aim 1) we will compare metabolic and hormonal profiles between subjects that develop stress hyperglycemia compared to controls. In an open-label format (Aim 2) we will assess whether exposure to dulaglutide is associated with a reduction in the frequency of stress hyperglycemia compared to placebo (primary endpoint). Prospectively, we will assess the association of candidate metabolites and metabolic pathways with the onset of stress hyperglycemia. Potential mechanisms underlying these associations will be explored by examining whether the associations of exposure to dulaglutide and prevention/improvement of glycemic control can be explained by changes in metabolic pathways (and key metabolites within these pathways) measured in plasma that occur between 3 days prior to surgery (baseline) and during the perioperative period. Addressing these research questions

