- **Risk/Importance Assessment:** The anticipated benefits of the proposed research study outweigh the potential risks to participating subjects. The potential for serious adverse effects is small and the potential benefit to society is high enough for the studies to proceed.

E.1.7 Data and Safety Monitoring Plan (DSMP): Please see DSMP provided as a separate document.

E.1.8 ClinicalTrials.gov Requirement: This clinical trial will be registered on ClinicalTrials.gov. Final results will be published on this site.

E.1.9 Statistical Considerations

Sample Size Calculation and Power Analysis: with a Wilcoxon test, for an effect size >1 at alpha=0.05 and power=0.80, the proposed sample size of N=50 for this experiment will be more than adequate for the main objective of identifying differentially expressed metabolites and pathways in Aim 1, as shown in previous studies.^{134,138} For Aim 2 we assumed N=60. No preliminary data on prevention of hyperglycemia is available. Assuming an effect size of ~0.50 on hyperglycemia prevention with χ^2 goodness of fit for contingency tables, power 80%, alpha=0.05, a total of 52 patients would be needed. In our previous RCT (GLUCO-CABG⁴) non-DM patients in the conservative group had a mean BG 143mg/dl vs. 127mg/dl in the intensive group. This difference was associated with a lower composite score of complications in the intensive group. It is reasonable to assume the standard deviation of the mean BG is bounded around 40 mg/dl. With two-sample t tests or Wilcoxon tests, alpha=0.05, 25 subjects for each arm would be needed to ensure 80% power to reject the hypothesis that the mean BG in patients treated with dulaglutide is not 16 mg/dl lower compared to placebo. Accounting for ~15% attrition rate this leads to a final total sample size estimate of 60 patients for both considerations. This study is not powered to assess differences in hospital complications between groups.

Research Timeline	Yr1	Yr2	Yr3	Yr4	Yr5
Aim 1. Case-Control					
Study initiation (IRB)	x				
Recruitment / sample collection	xx	xx	xxx	xx	
Lab assays / data processing				xxx	xxx
Analysis / manuscript preparation				xxx	xxx
Aim 2. Clinical Trial					
Study initiation (IRB)	x				
Randomization / sample collection	xx	xxx	xx	xx	
Lab assays / data processing				xxx	xxx
Analysis / manuscript preparation				xxx	xxx

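### The Aim 1 power statement is for a single test at alpha 0.05 and does not describe the Benjamini-Hochberg-corrected untargeted metabolite analysis that it is used to justify

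*Combined protocol and SAP*

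**What the plan says.** Section E.1.9 (Statistical Considerations) bases the Aim 1 sample size on one Wilcoxon calculation: "for an effect size >1 at alpha=0.05 and power=0.80, the proposed sample size of N=50 for this experiment will be more than adequate". The purpose it names is to find metabolites and pathways that differ between cases and controls. It cites two earlier studies in support. It does not mention multiplicity, and it does not say whether the test is one- or two-sided.

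The design is set out in D1 ("In a nested case-control study (N=50) we will compare the characteristics of patients developing postoperative stress-hyperglycemia (cases") and in E.1.1, Group Assignment / Case Definition ("25 age-matched controls will be selected for comparison"). Together these give 25 against 25.

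For the untargeted analysis, Aim 1.2 says: "Multiple hypotheses testing correction will be performed using the Benjamini-Hochberg method". No FDR level is given there or elsewhere. Section E.1.2 expects more than 2,000 measured intermediates, and C.6 reports 4,144 in the team's earlier work. The pitfalls paragraph for Aim 1 concedes: "It is possible that some comparisons do not yield false discovery rate (FDR)-significant metabolites". In that event metabolites with raw p<0.05 go forward to pathway enrichment.

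**The concern.** The power statement and the analysis use different rejection thresholds. A single test rejects at p<0.05. BH over thousands of features rejects at a data-dependent cut-off, which is much smaller when few features differ. Power at 0.05 is therefore not the chance that a truly different metabolite appears on the FDR-controlled list.

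This matters for interpretation. A reader who takes the 80% at face value will give too much weight to a metabolite's absence from that list. The documents also supply no figure from which the real sensitivity could be read.

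**Working it through.** **Inputs from the documents.** Wilcoxon test, effect size above 1, alpha 0.05, power 0.80 (E.1.9); 25 per group (D1, E.1.1); m above 2,000 features (E.1.2), or 4,144 as in C.6; BH correction (Aim 1.2).

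**Assumptions, because the documents are silent.** Effect size is read as the standardised mean difference d, taken first at its lower bound of 1. Tests are two-sided. The FDR level q is 0.05, 0.10 or 0.20. The share of truly different features (the non-null share) is 1%, 5%, 10% or 20%. The only related figure in the documents is in C.6, where 216/4,144 = 5.2% of features were significant in ketoacidosis patients. That is an imperfect proxy.

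**Step 1: the plan's own figure.** By the normal approximation, n per group = 2(1.960+0.842)²/d² = 15.7 at d=1, so 16. The t-test needs 17. The Wilcoxon test (relative efficiency 0.955) needs 18, or 36 in total; simulated power at 18 per group is 80.4%. At 25 per group the effective n is 25×0.955 = 23.9, the noncentrality is √(23.9/2) = 3.46 and power is 92.2% (simulated 92.0%). So N=50 exceeds the requirement for one test, and the stated calculation is correct on its own terms.

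**Step 2: the planned analysis.** BH rejects the k smallest p-values, with k the largest rank such that p(k) ≤ qk/m. Average power is the expected fraction of truly different features rejected. Wilcoxon p-values were simulated for 25 against 25 with independent normal features, at m=2,000 and m=4,144. The two values of m agree within a few percentage points, so they are pooled here:

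| Average power at d=1 | 1% differ | 5% | 10% | 20% |
|---|---|---|---|---|
| q=0.05 | 20% | 50% | 62% | 73% |
| q=0.10 | 32% | 63% | 74% | 83% |
| q=0.20 | 47% | 76% | 85% | 91% |

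**Step 3: cross-check.** In large samples the BH cut-off a solves a = q[(1−π)a + π·power(a)], where π is the non-null share. With q=0.05 and π=0.05 the solution is a=0.00138, where power is 0.525: 0.05×(0.95×0.00138 + 0.05×0.525) = 0.00138. The effective per-feature threshold is about 1/36 of the stated 0.05 (0.05/0.00138 = 36). This approximation runs a little above the simulation (27%, 53%, 64% and 74% at q=0.05).

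**Step 4: larger effects, q=0.05 (simulated).**

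| Average power | 1% differ | 5% | 10% |
|---|---|---|---|
| d=1.2 | 53–57% | 78% | 86% |
| d=1.5 | 90–91% | 96–97% | 98% |

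By the approximation in step 3, the smallest d with 80% average power at 25 per group is about 1.36, 1.20 and 1.12 for 1%, 5% and 10% differing. At q=0.20 it is about 1.20, 1.03 and 0.95.

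**Step 5: chance of an empty list.** At d=1 and q=0.05, the simulated chance of no BH discovery is about 0–13% when 1% or more of features differ, and at most about 38% at 0.5%.

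**The case against.** The strongest reply is that the shortfall rests on choices the authors never made. They state no FDR level, and they wrote an effect size above 1, not equal to 1. At d=1 with q=0.20 and 10% of features differing, average power is about 85%. At q=0.05 with 10% differing and d=1.2, it is about 86%. The objective also covers pathways, which have their own enrichment route, and Aim 1.1 is a targeted panel for which no BH correction is stated. All of this stands, and it limits the point to the FDR-controlled metabolite tests of Aim 1.2, with a range in place of a single value. The simulations also assume independent normal features and ignore the age-matching and repeated sampling times.

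The reply does not restore the adequacy claim. Whether 80% is reached depends on an FDR level and a non-null share that the plan does not state, and the power it does state is calculated at another threshold. The raw p<0.05 fallback does not close the gap either. It gains sensitivity by giving up FDR control: 2,000×0.05 = 100 false positives are expected if all 2,000 features are null.

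A reader might go further and infer three things that the figures do not support:

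- **That power falls short under every plausible assumption.** The tables show settings above 80%.
- **That most true features would be missed.** At d=1 and q=0.05 this is so at 1% differing. At 5% about half are found, and at 10% or 20% most are.
- **That the raw p<0.05 fallback becomes the likely route.** It applies only when a comparison yields nothing, and step 5 shows that this is not the likely outcome in any setting examined.

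**Conclusion.** The point holds for Aim 1.2 and is wrong as written. The single-test arithmetic is sound, so the error lies in applying it to an FDR-controlled search over thousands of features. At the lower-bound effect and an assumed 5% FDR, average power is about 20% to 73% for non-null shares of 1% to 20%, against about 92% for one test. Over all the FDR levels examined (5% to 20%), the range at d=1 is about 20% to 91%. These figures rest on the assumed FDR levels and non-null shares, two-sided tests, and independent normal features. They say nothing about the targeted panel or pathway enrichment.

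**What to change.** In E.1.9, limit the alpha 0.05 / 80% power statement to a single pre-named test, and remove the adequacy claim for Aim 1.2. In its place give:

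- the FDR level chosen by the authors;
- the assumed share of truly different features, with a range;
- the resulting average power, or the minimum detectable effect, for 25 against 25 with the Wilcoxon test;
- a note that independence and normality of features are assumed.

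If the authors choose a 5% FDR, the minimum detectable effect for 80% average power is about d=1.1 to 1.4 for 10% down to 1% of features differing.

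This is a change of wording only, and N stays at 50. The cost is a less favourable stated figure.

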C.2. GLUCO-CABG Trial:²⁴ in this RCT we aimed to determine whether intensive BG control (target: 100-140 mg/dl) could reduce perioperative complications compared to conservative BG control (141-180 mg/dl) in hyperglycemic patients undergoing CABG. A total of 302 patients were randomized to intensive (n=151) or conservative (n=151) glucose control. The mean ICU daily BG was 132 ± 14 mg/dl (IQR 124-139) in the intensive and 154 ± 20 mg/dl (IQR 142-164) in the conservative group ($p < 0.001$). Overall, we observed a similar number of patients in the intensive and conservative groups experiencing ≥ 1 complications (42% vs. 52%, $p = 0.08$). We observed no differences in the composite or individual complications in patients with DM; however, the composite of complications was lower in non-DM patients with stress-hyperglycemia assigned to the intensive group, $p = 0.008$, (Fig.2). Since all patients enrolled GLUCO-CABG patients had stress-hyperglycemia, we recently *analyzed phenotypic and biological characteristics of non-diabetic individuals at risk for perioperative stress hyperglycemia during CABG*. The two most important features in patients who developed >2 episodes of BG >140 mg/dL were older age (67.0 ± 9.2 vs 59.1 ± 9.4 , $p = 0.004$) and higher BMI (28.9 ± 5.8 vs 26.1 ± 4.3 , $p = 0.06$). All six patients older than 50 years and BMI >30 kg/m² developed hyperglycemia. These characteristics were confirmed in an additional cohort (i.e. age >45 years). Older age and obesity are well-established risk factors for insulin resistance and DM.

C.3. Inflammatory markers during CABG: Circulating levels of cortisol, inflammatory and oxidative stress markers increase for several days in the perioperative period (Fig. 3). No difference was observed between conservative and intensive insulin therapy groups in the perioperative period of patients undergoing CABG surgery. Changes in these markers did not explain the benefits associated with tighter glycemic control with insulin therapy.³

C.4. GLP-1 RA safety and non-inferiority to insulin therapy.

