Exclusion criteria: a) Hyperglycemia (BG > 125 mg/dl or HbA1c $> 6.5\%$) or previous treatment with antidiabetic agents; b) impaired renal function (GFR < 30 ml/min) or clinically significant hepatic failure; c) subjects with gastrointestinal obstruction expected to require gastrointestinal suction; d) patients with clinically relevant pancreatic or gallbladder disease; e) treatment with oral or injectable corticosteroid; f) mental condition rendering the subject unable to understand the possible consequences of the study; g) pregnancy or breast-feeding at time of enrollment. Additional considerations are outlined in the Human Subjects section.

Aim 2.1 Prevention of hyperglycemia (primary endpoint):

The primary endpoint of this exploratory study is to compare the frequency of stress-hyperglycemia defined as any post-CABG hospital-obtained BG > 140 mg/dl between patients randomized to dulaglutide or placebo.

Aim 2.2 Secondary Endpoints: To determine the difference between groups in mean BG level in the ICU.

Additional endpoints include differences between treatment groups on: 1) the number of patients with stress-hyperglycemia requiring rescue therapy with SC insulin after discontinuation of CII; 2) need for CII treatment of hyperglycemia in the ICU; 3) mean ICU and floor BG concentration; 4) mean insulin dose during ICU (insulin infusion per hour (unit/hour) and per day); 5) duration of CII (hours); 6) days of SC insulin after discontinuation of CII; 7) amount of SC insulin in ICU and non-ICU stay; 8) hyperglycemic events (BG ≥ 200 mg/dl) in ICU and non-ICU; 9) hypoglycemic events in ICU and non-ICU (< 70 , < 54 , and < 40 mg/dl); 10) composite of mortality and complications including sternal wound infection, bacteremia, pneumonia, acute kidney injury, and acute myocardial infarction; 11) gastrointestinal adverse events (nausea, vomiting, ileus, pancreatitis); 12) ICU and hospital LOS, and ICU readmissions; 13) cerebrovascular events; 14) ICU and hospital mortality.

Methods for Aims 2.1 and 2.2:

Treatment Groups: Patients will be randomized at pre-surgery/anesthesia visit. Patients without a history of DM will receive a single injection of dulaglutide/placebo 1-3 days prior to surgery (Fig. 8).

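### Aim 2 mean-BG sample size does not follow from its stated inputs: at SD 40 mg/dl and a 16 mg/dl difference, 25 per arm gives about 28% power, not 80%

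*Combined protocol and SAP*

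**What the plan says.** The calculation is in E.1.9 Statistical Considerations, under the sample size and power heading.

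- **Difference.** It comes from the earlier GLUCO-CABG trial: "non-DM patients in the conservative group had a mean BG 143mg/dl vs. 127mg/dl in the intensive group", i.e. 16 mg/dl.
- **Variability.** "It is reasonable to assume the standard deviation of the mean BG is bounded around 40 mg/dl".
- **Test and size.** With a two-sample t or Wilcoxon test at alpha 0.05, "25 subjects for each arm would be needed to ensure 80% power to reject the hypothesis". The hypothesis to be rejected is worded as dulaglutide failing to lower mean BG by 16 mg/dl relative to placebo.
- **Use.** After about 15% attrition, "this leads to a final total sample size estimate of 60 patients for both considerations". The other consideration is the binary primary endpoint, for which the section gives 52 patients in total.

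The endpoint itself is in Aim 2.2: "To determine the difference between groups in mean BG level in the ICU". The analysis paragraph for Aims 2.1 and 2.2 plans unadjusted two-sample t or Wilcoxon tests for continuous secondary outcomes.

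**The concern.** A difference of 16 against an SD of 40 is a standardised effect of 0.40. Twenty-five per arm is far too few to detect an effect of that size with 80% power, so either the SD or the number per arm is misstated.

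The plan presents this as one of two calculations that support 60 patients. If SD 40 is right, the trial would miss a true 16 mg/dl difference about 72% of the time. A reader who trusted the 80% could then take a null result as evidence against an effect. Aim 2 is meant to supply preliminary estimates for later trials, so a wrong SD would also carry forward into their design.

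**Working it through.** **Inputs, all from E.1.9 unless noted.** Difference 143 − 127 = 16 mg/dl; SD 40 mg/dl; alpha 0.05; power 80%; 25 per arm. Allocation is 1:1 (30 and 30, section E.1.1). Sidedness is not stated for this comparison. I take two-sided, as the plan states for the primary outcome, and check one-sided as well.

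**Step 1: try to reproduce 25 per arm.** The normal approximation is n per arm = 2 × (1.960 + 0.842)² × (SD/difference)².

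- SD 40: 2 × 7.849 × (40/16)² = 98.1, so 99 per arm. The exact noncentral t calculation gives 99.1, so 100 per arm. The stated 25 is not reproduced.
- SD 20: 2 × 7.849 × (20/16)² = 24.5, so 25 per arm. The exact t gives 25.5, so 26.

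The figure of 25 therefore fits an SD near 20, half the one stated. The document does not say where 25 comes from, so this is only an inference.

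**Step 2: power at the stated size and SD.** The standard error of the difference is 40 × √(2/25) = 11.3 mg/dl, and the noncentrality is 16/11.3 = 1.41 on 48 degrees of freedom. Two-sided power is 28.3%. With all 30 per arm evaluable it is 33.2%. Wilcoxon at 25 per arm gives about 27% (simulation with normal data).

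**Step 3: other readings at SD 40.**

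| Reading | Result |
|---|---|
| One-sided alpha 0.05 | 40% power at 25 per arm; 78 per arm for 80% |
| 40 taken as the SD of the between-arm difference | 50 per arm for 80% |
| Baseline adjustment, correlation 0.8 (not planned) | 36 per arm for 80% |
| Difference of 18 mg/dl (expected outcomes, Aim 2) | 34% power at 25 per arm; 40% at 30 per arm |

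None gives 25 per arm with 80% power.

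**Step 4: what 25 or 30 per arm can support.** The standardised difference detectable with 80% power is 0.809 at 25 per arm and 0.736 at 30 per arm.

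- At SD 40 these are 0.809 × 40 = 32.3 mg/dl and 0.736 × 40 = 29.4 mg/dl.
- For 16 mg/dl, the largest SD that still gives 80% is 16/0.809 = 19.8 mg/dl at 25 per arm and 16/0.736 = 21.8 mg/dl at 30 per arm.

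**Step 5: power for 16 mg/dl over a range of SDs (two-sided).**

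| SD (mg/dl) | t, 25 per arm | Wilcoxon, 25 per arm | t, 30 per arm | n per arm for 80% (t) |
|---|---|---|---|---|
| 40 | 28% | about 27% | 33% | 100 |
| 30 | 46% | about 43% | 53% | 57 |
| 25 | 60% | about 57% | 68% | 40 |
| 20 | 79% | about 76% | 86% | 26 |
| 17.3 | 89% | – | 94% | 20 |
| 14 | 98% | – | 99% | 14 |

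SDs 14 and 20 are those reported in C.2 for mean ICU daily BG in the two GLUCO-CABG arms. The equal-weight pooled value is √((14² + 20²)/2) = 17.3.

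**Step 6: precision.** The 95% confidence interval half-width at 25 per arm is 2.01 × SD × √(2/25): 22.7 mg/dl at SD 40 and 11.4 mg/dl at SD 20.

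The attrition step is sound: 50/0.85 = 58.8, in line with 60.

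**The case against.** **The SD of 40 is only a bound.** This does not repair the sentence. A size said to ensure 80% power has to deliver it at the bound, and no other SD is named in the calculation.

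**The trial may be adequately powered in fact.** This is the strongest point. The only observed SDs in the documents, 14 and 20 mg/dl in C.2, put power at 25 per arm between about 79% and 98%, so the slip may lie in the printed SD. It cannot be settled from the text, and E.1.9 does not cite those SDs for this purpose. They come from the whole earlier trial: "A total of 302 patients were randomized to intensive (n=151) or conservative (n=151) glucose control". That population included diabetes ("We observed no differences in the composite or individual complications in patients with DM"), and everyone was treated to an insulin target. No SD is given for the non-diabetic subgroup that supplies 143 and 127 mg/dl. The Aim 2 analysis paragraph also speaks of mean BG on ICU arrival, whereas Aim 2.2 refers to the ICU as a whole, and SDs of daily ICU means may not carry over to an arrival value.

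**The endpoint is secondary and the trial exploratory.** True. The primary endpoint has its own calculation of 52 patients, which reaches about 60 after attrition (52 × 1.15 = 59.8), so N=60 does not rest on mean BG alone. I have not assessed that calculation here. This limits the consequence but does not make the power statement correct, and the plan explicitly claims 60 for both purposes.

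**Conclusion.** The concern holds. Under the plan's own inputs, 25 per arm gives about 28% power for a 16 mg/dl difference, and 80% power needs about 100 per arm, four times the stated number. The result assumes a two-sided test, equal SDs in the two arms and the unadjusted analysis the plan describes; a one-sided test raises power only to about 40%.

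The actual power of the trial depends on an SD that the documents do not settle. It is about 79% if the SD is 20 mg/dl, higher if smaller, and falls quickly above that. What is certain is that the stated SD and the stated sample size contradict each other, and one of them must be corrected.

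**What to change.** Keep N=60 and rewrite the mean-BG sentences in E.1.9 in one of two ways.

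- **(a) Keep SD 40.** State that 25 evaluable patients per arm give about 28% power for 16 mg/dl, and 80% power only for about 32 mg/dl (about 29 mg/dl at 30 per arm).
- **(b) Use a smaller SD.** State it, justify it for non-diabetic patients and for the BG measure actually compared (ICU mean or arrival value), and give power at 25 per arm over the range: about 79% (SD 20), 60% (25), 46% (30), 28% (40). At SD 20, write about 79% (about 76% for Wilcoxon) and drop the claim to ensure 80%. If the C.2 SDs are used, note that they come from all 302 patients, with and without diabetes, treated to insulin targets.

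While editing, reconcile the 16 mg/dl here with the 18 mg/dl under the Aim 2 expected outcomes. Two smaller improvements are optional: word the null as no difference, with 16 mg/dl as the assumed true difference; and, since the aim is estimation, report the expected 95% confidence interval half-width (about 23 mg/dl at SD 40, 11 mg/dl at SD 20).

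The cost is one paragraph. No patients are added and the planned analysis does not change; the stated power becomes less favourable unless a smaller SD can be justified.
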